## 5.3. Recruitment Methods

All patients, aged  $\geq 18$  years old with a history of laboratory-confirmed SARS-CoV-2 infection via a positive molecular (RT-PCR) or antigen (lateral flow assay) test, receiving outpatient/inpatient care from [name] General Hospital (any time prior to enrolment in this study) are offered to be a participant in this study. One of the research team, dr. [name] will be examining the supervision of the primary investigator, dr. [name], DIC, Ph.D., SpPD, and study coordinator, dr. [name], SpPD.

## 5.4. Data Collection

Data on age, sex, height, weight, body mass index, income, education, comorbidities, smoking, alcohol consumption, documented SARS-CoV-2 vaccination

status (including the amount, type, and when the vaccine was received), detailed history of laboratory-confirmed SARS-CoV-2 infection, Long COVID symptoms, severity, and duration are collected through online screening questionnaire.

Data on quality of life (QoL) are collected through St George's Respiratory Questionnaire (SGRQ) and Short Form (SF)-36 Health Survey self-assessment questionnaire at baseline, 3 and 6 months after enrollment. SGRQ addresses QoL in the domains of symptoms, activity, and impacts within the last 4 weeks; and the SF-36 Health Survey questionnaire addresses QoL in the domains of vitality, physical functioning, bodily pain, general health perceptions, physical and emotional and social role functioning.

Data on functional exercise capacity is measured using the Six-Minute Walking Test (6MWT) at baseline, 3 and 6 months after enrollment. The 6MWT is performed according to the guidelines of the American Thoracic Society (ATS). During the 6MWT, such data are collected: Blood pressure, oxygen saturation (SpO2), heart rate, dyspnea, and overall fatigue score using the Modified Borg scale before and after the test, and also one-time measurement (total distance walked in 6 minutes, symptoms at the end of exercise).

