## **STUDY PROTOCOL**

### **1. Introduction**

Long COVID is defined by the persistence or emergence of symptoms for more than 4 weeks beyond the acute phase of Severe Acute Respiratory Syndrome-Corona Virus-2 (SARS-CoV-2) infection. As the number of cases increases and various strains of SARS-CoV-2 emerge, so does the number of long COVID cases. Various multi-organ complications after COVID-19 infection include respiratory, cardiovascular, gastrointestinal, hepatobiliary, metabolic, and neuropsychiatric disorders. The symptoms and characteristics of Long COVID vary in each country.

Vaccination against SARS-CoV-2 has been documented to increase the clinical resolution of Long COVID. In Indonesia, current full-dose vaccination coverage had merely reached 15.6% of the national vaccination target. This condition can be predictably associated with a longer duration and higher severity of symptoms in Long COVID patients.

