#### **2.2. Secondary**

- To determine whether vaccination against SARS-CoV-2 could increase functional exercise capacity of Long COVID patients at [name] General Hospital.
- To determine whether vaccination against SARS-CoV-2 could reduce symptoms, duration, and frequency of Long COVID at [name] General Hospital.

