#### 5. Methods

##### 5.1. Study Design

This is a prospective cohort, cross-sectional study involving two hundred and fifty (250) subjects of post-acute COVID-19 patients, receiving outpatient/inpatient care from [name] General Hospital during the acute phase of the infection, any time prior to enrollment in this study.

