## 5.2. Study Population and Selection Criteria

All participants will be required to sign a written informed consent, be willing and able to comply with all study requirements, and should meet the following criteria:

1. Adult patients, aged  $\geq 18$  years old with a history of laboratory-confirmed SARS-CoV-2 infection via a positive molecular (RT-PCR) or antigen (lateral flow assay) test, receiving outpatient/inpatient care from [name] General Hospital, any time prior to enrollment in this study
2. Patients with/without comorbidities
3. Willing to fill-out online Long COVID symptoms follow-up questionnaire
4. Willing and able to comply with trial protocol (re-visits and physical testing)

Subjects will be **excluded** from the study based on the following criteria:

1. Patients with no registered medical record number (MRN) at [name] General Hospital
2. Refusal to participate in the study or to sign the informed consent form
3. Any contraindications for 6 Minute Walking Test according to the guidelines of the American Thoracic Society (ATS)
4. Patients with no access to a smartphone or computer (desktop, laptop, or tablet) to fill out the online screening questionnaire
5. Patients who died during or before enrollment in the study

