##### **3.2.2. Bivariate analysis**

This analysis is used to see the relationship between the effect of the COVID-19 vaccine on clinical long COVID and the quality of life of long COVID patients. The level of significance used is 0.05. Variables are statistically significant if p-value <0.05. The independent variables in this study are nominal scale, so the test used in this analysis is the chi-square test or fisher's test (in the group of independent variables with a dichotomous scale of 2x2 if the chi-square does not meet the requirements.

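### For subjects still symptomatic when last asked, Long COVID duration is only the time elapsed since infection; that time is unrestricted, and the chi-square/Fisher plan cannot handle it

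*Combined protocol and SAP*

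**What the plan says.** Protocol section 2.2 asks whether vaccination "could reduce symptoms, duration, and frequency of Long COVID", so duration is an outcome to be compared by vaccination status. The introduction defines the condition as "persistence or emergence of symptoms for more than 4 weeks beyond the acute phase", which sets a minimum but no time at which duration is fixed.

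On measurement, section 5.4 states that "Long COVID symptoms, severity, and duration are collected through online screening questionnaire". The measures it schedules at baseline and at months 3 and 6 are SGRQ, SF-36 and the walking test. An inclusion criterion in section 5.2 mentions an online symptom follow-up questionnaire, but neither its content nor its timing is given.

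On timing, section 5.2 admits subjects infected "any time prior to enrollment in this study", and section 5.1 uses the same open window. There is no minimum, maximum or matching on time since infection, and follow-up visits are counted from enrolment. Section 5.4 does collect a "detailed history of laboratory-confirmed SARS-CoV-2 infection" and the dates of vaccination, but no stated analysis uses either.

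On analysis, SAP 3.2.2 says "the test used in this analysis is the chi-square test or fisher's test". The synopsis names the same tests. The text contains no censoring rule, time-to-event method, stratification or adjustment for time since infection.

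**The concern.** A resolved episode has a duration, apart from recall error. An ongoing episode has only a lower bound, equal to the time elapsed so far. Someone infected 2 months before the last questionnaire cannot report more than 2 months; someone infected 18 months before can. Tabulating both as complete durations mixes length of illness with length of observation.

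If one vaccination group was on average infected more recently, its recorded durations will be shorter for that reason alone. The result would read as a vaccine benefit, or as harm if the imbalance runs the other way. The synopsis expects the study to reinforce vaccine recommendations, so an artefact in the expected direction could go unchallenged.

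**Working it through.** **1. The plan's own figure.** The documents state no figure for duration or elapsed time. I borrow the SAP section 2 group size, which reproduces from its printed inputs:

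n = [(1.96·√(2·0.553·0.447) + 0.80·√(0.653·0.347 + 0.453·0.547)) / 0.20]² = [(1.378 + 0.551) / 0.20]² = 93.04, so 93 per group and 186 in total; 186 × 1.2 = 223.

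The point does not depend on this number.

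**2. Assumptions (mine, not the documents').** True duration T is exponential with mean 6 months in both groups, so there is no vaccine effect. Time since infection at screening, E, is uniform over a window that may differ between groups. Duration is split at a cut-off c and tested by uncorrected chi-square at 0.05. The plan gives no cut-off.

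**3. Mean recorded duration if read t months after infection.** E[min(T,t)] = 6(1 − e^(−t/6)):
- t = 3: 2.36 months
- t = 6: 3.79 months
- t = 12: 5.19 months

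The true mean is 6 months throughout.

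**4. Proportion recorded above the cut-off.** This is e^(−c/6) × P(observed longer than c). Example: c = 3, read at screening only, E = 1–6 versus 6–18 months.
- First group: 0.607 × 3/5 = 0.364
- Second group: 0.607 × 1 = 0.607
- Difference 0.243; standard error √(2 × 0.485 × 0.515 / 93) = 0.073; ratio 3.31
- Approximate rejection probability Φ(3.31 − 1.96) = 0.91. Simulation gives 92%.

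**5. False-positive rates** (20,000 simulated trials, 93 per group):

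| Months since infection at screening | Screening only, cut 3: proportions | Rejects | Followed to month 6, cut 3 or 6: rejects | Followed to month 6, cut 12: proportions | Rejects |
|---|---|---|---|---|---|
| 1–12 vs 1–12 | 0.496 vs 0.496 | 5% | about 5% | 0.074 vs 0.074 | 5% |
| 1–12 vs 1–18 | 0.496 vs 0.535 | 8% | about 5% | 0.074 vs 0.096 | 8% |
| 1–12 vs 3–18 | 0.496 vs 0.607 | 32% | about 5% | 0.074 vs 0.108 | 13% |
| 1–9 vs 3–18 | 0.455 vs 0.607 | 54% | about 5% | 0.051 vs 0.108 | 31% |
| 1–6 vs 6–18 | 0.364 vs 0.607 | 92% | about 5% | 0 vs 0.135 | over 99% |

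With follow-up to month 6, everyone in these windows is observed for at least 7 months, so cut-offs of 3 and 6 months are unaffected. A 12-month cut-off still is.

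**6. Sensitivity to the assumed mean.** With windows of 6–20 versus 2–12 months, screening only and a 6-month cut-off, rejection is 35%, 61% and 82% for true means of 4, 6 and 9 months.

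**7. Does a fixed time point cure it?** Keeping only subjects observed for at least 3 months and comparing the proportion still symptomatic at 3 months brings every row of the table back to about 5%, even with screening data alone.

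**The case against.** **Symptoms may be re-asked.** The inclusion criteria name a symptom follow-up questionnaire, and visits occur at months 3 and 6. If it captures ongoing or resolved status to month 6, the inflation disappears at 3- and 6-month cut-offs. This stands as a limit on the size. It does not dispose of the point, because the documents schedule no repeat of duration and a later cut-off remains affected.

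**The timeline may rule out recent infections.** Section 4 places record collection in November–December 2021 and questionnaires from March 2022. If the cohort comes from those records, nearly everyone is about 3 months or more past infection. With windows of 3–9 versus 6–18 months and a 3-month cut-off, rejection is then about 5%. But section 5.2 allows a wider reading, and the protection ends at the cut-off. At 6 months the proportions are 0.368 × 0.5 = 0.184 versus 0.368, the ratio to the standard error is 0.184 / 0.066 = 2.8, and rejection is about 80%.

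**The plan never says how duration is categorised or tested.** True: the 3-month cut-off is mine, and SAP 3.2.2 does not name duration. The figure under SAP 3.2 was not available to me. Still, the text offers no other method for this objective.

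**Randomisation would balance elapsed time.** SAP section 1 mentions block randomisation, but groups are defined by documented vaccination history, which cannot be allocated.

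**Tempting stronger readings.** A reader might infer that, because third doses come later in calendar time, three-dose subjects were infected more recently and the bias favours vaccination. The documents do not support this: that argument concerns dose dates, and nothing requires doses to precede infection or links dose count to infection date. A reader might also infer that every duration is cut off. Eligibility does not require current symptoms, so subjects already recovered can report complete durations.

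**Conclusion.** The point holds in limited form. Recorded duration is censored for subjects still symptomatic at last contact, the censoring time is unrestricted, and the stated tests cannot account for it. A false difference then needs time since infection to differ between vaccination groups. Nothing in the plan prevents that, but nothing shows that it will occur.

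The 8% to 92% rates under unequal windows are conditional illustrations and should not be read as expected error rates. They rest on an assumed exponential mean of 6 months, assumed windows, a 3-month cut-off and no repeat of the symptom questions. With equal windows the rate is 5%. With symptoms followed to month 6, inflation remains only at late cut-offs. Size and direction in this study are unknown.

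One component of one secondary objective is affected. The plan should be changed, because the remedy is cheap and uses dates already being collected, but the point does not undermine the study as a whole.

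**What to change.** **Section 5.4.** At screening and at months 3 and 6, record whether symptoms are resolved or ongoing and, if resolved, the date.

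**SAP 3.2.2.** State that raw elapsed durations will not be compared, and choose one of the following:

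- (a) Compare the proportion still symptomatic at one fixed time after infection (for example 3 months), using only subjects infected at least that long before their last questionnaire. Define vaccination group by doses received before infection. Chi-square or Fisher can be kept.
- (b) Analyse time from infection to resolution, with ongoing symptoms censored at the last questionnaire (Kaplan-Meier with log-rank, or Cox). Either classify vaccination by doses before infection, or enter it in a Cox model as a time-dependent covariate using the recorded dose dates.

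The condition on vaccination timing is essential. Grouping time from infection by final dose count would credit symptomatic time before a later dose to the vaccinated group, replacing one bias with another (immortal time).

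**Cost.** One questionnaire item asked three times, plus SAP wording. Under (a), subjects whose last questionnaire falls before the fixed time leave that comparison. Where groups are defined by doses before infection, subjects vaccinated only afterwards are reclassified for this one outcome.

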## **5.5. Expected Outcomes**

It is the investigator's expectation that vaccination against SARS-CoV-2 could improve clinical outcomes and quality of life; and reduce symptoms, duration, and frequency of Long COVID.

## **5.6. Adverse Reactions**

There is no expectation of any adverse outcomes or reactions, should there be any adverse outcome or reactions, necessary management and will be taken in accordance with the standard medical protocol at the [name] General Hospital. All participants will be given access to the contact information of the research team performing this study. Any adverse reactions will be reported immediately to the primary investigator or study coordinator.

## **6. Potential Benefits and Risks**

The 6MWT is a safe test with rare complications. It is a practical, simple test that requires, in ideal circumstances, a 100-foot hallway, no exercise equipment, and no advanced training for technicians. Walking is a daily activity for all but severely

impaired patients and so can be used by most patients in a practice. Patient involvement is based on voluntary participation, is self-directed, and is easily terminated in the event of a complication.

Safety considerations when administering the 6MWT include both technical and clinical aspects. Technical aspects for safety include proper training and knowledge for the person administering the test, adequate facility provision, and emergency provisions. Clinical aspects of safety considerations for the 6MWT include knowledge of absolute and relative contraindications and conditions requiring immediate cessation of the 6MWT. Study documentation of adverse effects reveals oxygen desaturation as the most common adverse effect, with desaturation to less than or equal to 80% in approximately 5% of testing, and patient symptoms prematurely terminating the test in 1% of testing. The absolute contraindications are unstable angina and/or myocardial infarction in the past 30 days. The relative contraindications are resting heart rate above 120 bpm, systolic blood pressure over 180 mmHg, and diastolic blood pressure above 100 mmHg. The reasons for cessation according to the ATS guideline are sudden chest pain, intolerable dyspnoea, leg cramps, staggering, diaphoresis, and pale or ashen appearance.

We take extra effort during the study period to maximize patient safety. Fulfilling this goal, the study staff employs stringent procedures to reduce the risk of adverse events during the study period.

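### Section 6 reports desaturation to 80% or less in about 5% of walking tests and symptom stops in 1%, yet its list of reasons to stop the walk contains no SpO2 level.

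*Combined protocol and SAP*

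**What the plan says.** Protocol Section 6 (Potential Benefits and Risks) describes the known hazards of the 6MWT. It reports "oxygen desaturation as the most common adverse effect, with desaturation to less than or equal to 80% in approximately 5% of testing" and, in the same sentence, "patient symptoms prematurely terminating the test in 1% of testing". It gives no source population for either rate. Its stop list, presented as the American Thoracic Society (ATS) guideline's, is: "The reasons for cessation according to the ATS guideline are sudden chest pain, intolerable dyspnoea, leg cramps, staggering, diaphoresis, and pale or ashen appearance".

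Section 5.4 (Data Collection) schedules the test at baseline, 3 months and 6 months, performed under the ATS guideline. Its sentence on measurements opens "During the 6MWT, such data are collected: Blood pressure, oxygen saturation" and closes "overall fatigue score using the Modified Borg scale before and after the test". The opening suggests readings in the course of the walk. The closing words attach the whole list to the times before and after it, and that is the more natural reading.

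Three other places bear on safety. The Synopsis (Safety Evaluations) sends management of adverse events to the ATS 6MWT guideline. Section 5.6 sends it to the hospital's standard protocol. Section 9 lets the investigator discontinue a subject whenever continuing is not in that subject's interest. None of them states a saturation level.

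**The concern.** Section 6 itself treats knowledge of the conditions that require immediate cessation as part of clinical safety, so the stop list is a working safety control. The hazard that the section ranks first has no entry in it. Each of the six reasons depends on the participant feeling something or on staff seeing something, and Section 6's own rates suggest that deep desaturation is more frequent than symptom stops.

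If SpO2 is read only before and after, staff cannot see a fall while it happens. If it is read during the walk, they have no value to act on. Either way, a participant at 80% or less who shows none of the six signs may keep walking under the list as written.

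The 6MWT is the only physical test described in Section 5.4. It is done up to three times, in patients whose disease has respiratory complications according to the Introduction. The point concerns what staff do during the test and does not affect the vaccination comparisons in the SAP.

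**Working it through.** **Inputs**
- Desaturation to 80% or less: about 5% of tests (Section 6).
- Early stops for patient symptoms: 1% of tests (Section 6).
- Tests per subject: 3 (Section 5.4).
- Subjects: 250 (Synopsis; Section 5.1) or 223 (SAP Section 2).
- Loss to follow-up: 20% (SAP Section 2). I assume that those lost miss both follow-up walks.

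**Step 1. The stated rates.** 5% / 1% = 5, so deep desaturation is about five times as frequent as symptom stops.

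**Step 2. Number of tests**
- 250 enrolled, full attendance: 250 × 3 = 750
- 223 enrolled, full attendance: 223 × 3 = 669
- 250 enrolled, 20% lost: 250 + 2 × 200 = 650
- 223 enrolled, 20% lost: 223 + 2 × 178.4 = 579.8

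**Step 3. Expected walks.** The third column is the smallest possible number of desaturations without a symptom stop. It assumes that every symptom stop is also a desaturation: 5% − 1% = 4%.

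| Tests | 80% or less (5%) | Without a symptom stop (4%) |
|---|---|---|
| 750 | 37.5 | 30.0 |
| 669 | 33.45 | 26.76 |
| 650 | 32.5 | 26.0 |
| 579.8 | 28.99 | 23.19 |

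So about 29 to 38 walks reach 80% or less. About 23 to 30 of them, at the least, have no listed reason to stop, **provided the 1% counts stops for all six listed reasons**. These are walks, not people. If the same participants desaturated at every visit, with full attendance, about 11 to 13 people would be involved (223 × 0.05 = 11.15; 250 × 0.05 = 12.5).

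**Step 4. How far the 4% depends on its assumptions.** The floor is the desaturation rate minus the rate of stops for any listed reason.
- Stops for any listed reason at 2%: 5% − 2% = 3%, or 17.4 to 22.5 walks.
- Stops at 3%: 5% − 3% = 2%, or 11.6 to 15.0 walks.
- Stops at 5%: the floor is zero, with desaturation unchanged.
- Desaturation halved, stops at 1%: 2.5% − 1% = 1.5%, or 8.7 to 11.25 walks.

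**Step 5. Search for a level elsewhere.** The Synopsis, the entry criteria (5.2), 5.4, 5.6 and Section 9 contain no SpO2 value that prompts action.

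**The case against.** The strongest reply is that the ATS guideline is incorporated by reference. The test is performed under it, contraindications are taken from it, and adverse events are managed by it. Desaturation is an adverse effect in Section 6's own words, so its management already has a home. Staff also have discretion: Section 6 says the test "is easily terminated in the event of a complication", and Section 9 allows discontinuation at any time.

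This stands in part. The guideline is not among the documents, so nobody can infer from them that it is silent on oxygen. But Section 6 states what it takes the guideline's reasons for cessation to be, and that is the list staff would follow. Rules on managing an event, and discretion to stop, do not say at what saturation a walk ends. Discretion also needs a reading to act on.

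Four stronger readings are tempting, and the documents do not support them.
- *At least 23 to 30 unprotected walks as a firm minimum.* The 1% is for patient symptoms. Staggering, diaphoresis and pallor are signs that staff observe, and stops for them may not be counted in it. As Step 4 shows, a higher total stop rate lowers the floor, to zero at 5%.
- *A participant with very low resting SpO2 may start the walk.* Section 6 lists "The absolute contraindications are unstable angina and/or myocardial infarction in the past 30 days" and "The relative contraindications are resting heart rate above 120 bpm, systolic blood pressure over 180 mmHg, and diastolic blood pressure above 100 mmHg", without oxygen. It neither attributes those lists to the guideline nor calls them complete, and Sections 5.2 and 9 defer contraindications to the guideline. The gap at the start of the walk is not established.
- *Falls to 80% or less are the most common adverse effect.* Section 6 says this of desaturation in general; 80% or less is the part for which it gives a rate.
- *Participants will be injured.* The documents give no injury rate, and Section 6 calls complications rare.

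It is also fair to object that 80% appears in Section 6 as a reporting cut-point and not as a safety threshold. It is offered below only as the one SpO2 figure in the protocol.

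**Conclusion.** The point holds for the stop rule. The protocol names oxygen desaturation as the leading 6MWT adverse effect, gives a rate for its severe form, and then lists reasons to stop that include no saturation level. At its own rates, about 29 to 38 walks would reach 80% or less. About 23 to 30 or more of these would lack a listed reason to stop if the 1% covers all six reasons, and possibly fewer if it does not.

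The counts rest on the 5% and 1% applying to this cohort, for which the documents give no evidence. The gap in the list does not depend on the counts. It is a low-cost improvement to participant safety and leaves the SAP's tests and sample size as they are.

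**What to change.** 1. **Section 6:** add to the reasons for cessation *SpO2 of 80% or less at any reading during the walk*. The investigators should confirm this level against the guideline and may set a higher one.
2. **Section 5.4:** state that SpO2 is read during the walk as well as before and after it.
3. **Case report form:** record the time, reason and distance at any stop, and use that distance as the visit's result.
4. **Section 9:** state that a stopped walk is not a drop-out, so questionnaires and later visits continue.
5. **Reporting:** tabulate oxygen stops by visit and vaccination group.

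**Cost.** A few sentences and one form field. If SpO2 is now read only before and after, wearing an oximeter during the walk is an added procedure. Up to about 5% of walks would end early at the 80% level. A higher level would end more, and the documents give no rate for that.

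If stopped walks end halfway and would otherwise have been average, mean distance falls by 0.04 × 0.5 = 2.0% to 0.05 × 0.5 = 2.5%. Distance measures functional exercise capacity, a secondary objective. On the same assumption, each percentage point by which oxygen stops differ between vaccination groups moves the group difference by about 0.01 × 0.5 = 0.5% of mean distance. Item 5 makes that visible.

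**Optional clarifications, not part of this point:** state a resting SpO2 below which that day's walk is postponed, and align the opening of Section 5.6, which expects no adverse outcomes, with Section 6.
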